**Randomization.** Randomization to the narrative intervention or usual care will occur at the patient level. The random allocation sequence will be computer generated using random block sizes, an allocation ratio of 1:1, and stratification by illness group. The project statistician will generate the allocation sequence using SAS software and the allocation sequence will be uploaded for study use into REDCap. Upon study completion, baseline characteristics between intervention and control patients will be compared using independent samples t-tests (continuous measures) and chi-square tests (categorical measures). Though balance is assumed, statistical adjustment will be used in outcome analyses in the event of pre-treatment differences between conditions.

**Data collection.** All survey and demographic data will be captured using electronic surveys through REDCap on password-protected iPads/laptops.

**Demographics.** At baseline, age, gender, race/ethnicity, education in years, income level, religion/spirituality preference, and clinical details to identify co-morbidities and severity of illness will be collected for all participating patients. This demographic detail will allow description of outcome means and standard deviations in key patient subgroups, including groups defined by patient race/ethnicity and specific chronic illnesses of heart disease or end-stage renal disease.

**Measures.** For Aim 1, the primary and secondary outcome measures will be collected at three time points from all patient participants. (Table 1). The purpose of these times periods are to collect the outcome measures consistently for usual care and intervention participants. This is based on knowledge gained during the K99 study regarding time to complete the narrative intervention. In the K99 study, for the narrative intervention, on average it took 24 hours post narrative interview to upload the patient's narrative into the EHR.

**Exit Interviews and Usability Scale.** For Aim 2, the patient and nurse exit interviews and system usability surveys from the nurses will be collected approximately 1-week post intervention. (Table 1).

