**Sample Size and Power Analysis.** Sample size estimates were generated to determine power to detect a time by treatment interaction within the proposed repeated measures design. Assuming two-sided alpha = 0.05, a sample size of 80 patients will provide 80% power to detect an effect size associated with treatment effects on changes over time as small as  $f=.14$  (Cohen's  $d = 0.28$ ). This represents a small, clinically relevant effect, but more importantly will provide stable measures of outcome means and standard deviations over time for use in the planned R01 efficacy trial. Modern missing data techniques will be used if patients drop out before all follow-up data is obtained. To minimize concerns for attrition, the time between baseline and follow-up data collection is small. Nonetheless, if patients are lost to follow-up, even if a high level of attrition (e.g., 20%) will allow for the detection of a small effect size of  $f=.16$ .

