Intervention group: Data collection activities for patients include completing demographic and outcomes measures at baseline (enrollment). Then, they will have outcome measures collected immediately after narrative upload into the EHR (approximately 24 hours after narrative is collected), and 24-48 hours post narrative upload into the EHR. For the narrative intervention group, a one-time audio recorded interview (60-90 minutes) with the research team member will occur once baseline measures have been collected. In addition, the intervention participants will participate in a second audio-recorded audio exit interview (30 minutes) and will collect information on acceptability and feasibility of intervention. This interview will be collected in the private location of the patient's hospital room or may be collected and recorded over the telephone if patient has been discharged from the hospital.

Usual care group: Data collection activities for these patients include completing demographic and outcomes measures only at baseline (at enrollment), and again 24-48 hours after enrollment.

*Outcome Measures:* The estimated time for completion of the 64 items on the questionnaires is approximately 30 minutes. The following questionnaires are included as the outcome measures: Quality of Communication (QOC) which consists of 19 items; PROMIS-29 Profile v.2.1 of 29 items each; and PROMIS Psychosocial Illness Impact {Negative and Positive} Short-Form 8a which consist of 16 items.

*Nurses:* Data collection activities for the nurse participants will include completing a 30 minute exit interview via an audio recorded interview. For the usability testing, data collection will include testing of the EHR interface with the bedside nurses and completion of a short questionnaire at the end of the 30 minute exit interview.

Data collection activities for intervention patient participants include:

1. Completing baseline outcomes measures and demographic information, approximately 30 minutes
2. Completing the narrative intervention via a 60-90-minute audio-recorded interview
3. Completing outcome measures after narrative upload
4. Completing outcome measures 24-48 hours after narrative upload
5. Completing an exit interview via a 30-minute audio-recorded interview.

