## F. Data Analysis Plan.

**Aim 1 Analysis Plan.** Statistical analyses will be performed with the use of SAS software, version 9.4. In preliminary analyses, data will be screened for errors and outliers; appropriate transformations will be made for non-normal outcomes. Baseline demographics will be summarized using standard descriptive statistics. The pattern of participant dropout will be examined to ensure a reasonable equal distribution of participants lost to follow-up between groups and based on baseline characteristics. Maximum likelihood techniques will include participants with incomplete data without need for imputation. In addition, we will conduct sensitivity analyses to examine the effect of departures from key assumptions made in the main analysis and to help determine effects of missing data. Using an intent-to-treat approach, primary and secondary outcomes will be analyzed with linear mixed models using SAS Proc Mixed to compare the two groups (narrative intervention versus usual care) over the assessment period. Separate models will be estimated for each of the primary and secondary outcomes, though relationships among outcomes will also be assessed. Mixed models will specify intervention group and time as fixed effects and subject as a random effect. Pairwise comparisons testing group effects at each time point are proposed to disentangle the effects of intervention process versus change in quality of communication between patient and nurse. All statistical analyses will be done in consultation with the project statistician, [name].

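### Separate group tests at Time 2 and Time 3 cannot separate the intervention process from a change in nurse communication; the plan needs an estimate of how the group difference changes between those visits

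*Combined protocol and SAP*

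**What the plan says.** The Aim 1 Analysis Plan (section F) gives both a method and a purpose: "Pairwise comparisons testing group effects at each time point are proposed to disentangle the effects of intervention process versus change in quality of communication". The communication in question is the patient's with the nurse. The plan names no contrast between visits and no rule for reading the visit results together. On the model it says: "Mixed models will specify intervention group and time as fixed effects and subject as a random effect". A group-by-time term is not named, although Sample Size and Power Analysis (section C) states: "Sample size estimates were generated to determine power to detect a time by treatment interaction within the proposed repeated measures design".

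On timing, the Narrative Intervention group paragraph (section C) has the patient tell, review and approve the narrative before upload; the assigned nurse is alerted once it is uploaded. For the intervention arm, section D part a says: "Then, they will have outcome measures collected immediately after narrative upload into the EHR". The next assessment there comes 24 to 48 hours after upload.

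Two descriptions do not agree:

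- **Time 2.** Table 1 puts it 24 to 48 hours after baseline or upload. Section D part a puts it immediately after upload.
- **Usual-care follow-ups.** Section D part a lists baseline and one follow-up at 24 to 48 hours. The Measures paragraph (section C) and the Quantitative Data paragraph (section D part b) give all patients three assessments.

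**The concern.** Write D2 and D3 for the true differences between groups at Time 2 and Time 3. The plan's question is whether communication changes beyond the effect of taking part in the story-telling. If the process effect is present by Time 2 and nurses use the narrative mainly afterwards, that question concerns D3 − D2. The planned tests address D2 = 0 and D3 = 0, one visit at a time. D3 contains whatever process effect remains plus any nurse effect, and a test of D3 = 0 cannot tell them apart. Setting one p-value beside the other does not help, because a non-significant Time 2 result is weak evidence of no process effect with 40 patients per arm.

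A process effect is plausible on the protocol's own account. The Significance section links taking part in narrative interventions to less pain, stress, anxiety and fatigue, and section E says patients cannot be blinded. At stake is what the study can tell the planned efficacy trial about how the intervention works. The total effect against usual care, which is Aim 1, is not affected.

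**Working it through.** **Inputs from the documents.** N = 80, 40 per arm (section D part a); two-sided alpha 0.05, 80% power, f = .14 (d = 0.28), and f = .16 with 20% attrition (Sample Size and Power Analysis); three assessments (Measures).

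**Assumed, not in the documents.** SD 1 at each visit; equal correlation r between visits, 0.5 to 0.8; a constant process effect of 0.28 to 0.6 SD. The lower end is the plan's d, used here as a difference at one visit.

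**1. The plan's own figure.** For a group-by-time interaction with m = 3 visits, sphericity and r = 0.5, λ = f²·N·m/(1 − r).

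- N = 80, f = .14: λ = 0.0196 × 80 × 3 / 0.5 = 9.41; df 2 and 156; power 78.2%. The smallest f with 80% power is .143, which rounds to .14.
- N = 64, f = .16: λ = 0.0256 × 64 × 3 / 0.5 = 9.83; df 2 and 124; power 79.8%.

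The stated figures are reproduced under that assumed correlation. This interaction is an omnibus test over three visits, so a lasting effect that starts at Time 2 would trigger it too. It does not answer the process-versus-nurse question either.

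**2. Test at one visit, process effect only.** Two-sample t test, 78 df, noncentrality d/√(2/40) = 4.472·d.

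| Process effect (SD) | Noncentrality | Time 3 test rejects, 40 per arm | 32 per arm (20% loss) |
|---|---|---|---|
| 0.28 | 1.25 | 23.5% | 19.7% |
| 0.3 | 1.34 | 26.3% | 21.9% |
| 0.5 | 2.24 | 59.8% | 50.4% |
| 0.6 | 2.68 | 75.5% | 65.6% |

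These figures are power for a real total effect. They mislead only if a Time 3 rejection is read as a nurse effect. The Time 2 test has the same power, so at 40 per arm it misses a 0.5 SD process effect 100 − 59.8 = 40.2% of the time.

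**3. The two tests read together, process effect only.** Share of simulated trials (40 per arm) with Time 2 not significant and Time 3 significant:

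| Process effect (SD) | r = 0.5 | r = 0.7 | r = 0.8 |
|---|---|---|---|
| 0.28 | 13% | 10% | 8% |
| 0.3 | 13% | 10% | 8% |
| 0.5 | 16% | 12% | 10% |
| 0.6 | 13% | 10% | 8% |

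In the same trials, a t test of the group difference in (Time 3 − Time 2) rejects in about 5% in every cell.

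**4. Power of the direct contrast.** The variance of a Time 3 − Time 2 change is 2(1 − r), so the standardised effect is δ/√(2(1 − r)). For δ = 0.28 this is 0.28, 0.36 and 0.44 at r = 0.5, 0.7 and 0.8.

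| Added nurse effect after Time 2 (SD) | r = 0.5 | r = 0.7 | r = 0.8 |
|---|---|---|---|
| 0.28 | 24% | 36% | 50% |
| 0.5 | 60% | 81% | 94% |

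When a 0.5 SD nurse effect is added to a 0.5 SD process effect, the pattern in step 3 appears in only about 40% of trials. In most of the rest both visits are significant, which looks the same as process alone.

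**5. Sensitivity to timing.** If half of a 0.5 SD nurse effect is already present at Time 2, the contrast sees δ = 0.25, and its power falls to 20% (r = 0.5) or 42% (r = 0.8).

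**The case against.** A reader might infer from step 2 that the plan carries a false-positive rate of 24% to 75% for a nurse effect. The documents do not support that. The plan never says a Time 3 rejection alone will be read as a nurse effect, and the range depends on assumed effect sizes. The 8% to 16% for the two-visit pattern is the closer figure, and it too is an illustration.

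A reader might also take a process effect on the primary outcome as established. The protocol's evidence concerns symptoms, psychosocial outcomes and quality of life; the primary outcome is rated communication with nurses. An effect of story-telling alone on that rating is possible, but the documents do not quantify it.

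Nor may the Time 2 to Time 3 contrast be treated as the only valid evidence on communication. It assumes a stable process effect and little nurse exposure before Time 2. A fading or growing process effect would bias it, and Table 1 allows nurses to have read the narrative by Time 2.

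Finally, this is a proof-of-concept study. Exit interviews and the usability work also bear on nurse use, and section E already points to an active control for later studies. That lowers the stakes. What stands is that the method named for the stated purpose cannot deliver it.

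**Conclusion.** The point holds. Separate tests by visit cannot disentangle process from nurse communication, because the Time 3 difference includes any persisting process effect and the change in the difference is never tested. This follows from the order of events in the protocol and needs no assumed effect size.

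The size does need assumptions: 40 per arm, a constant process effect of 0.28 to 0.6 SD, no nurse effect, and r of 0.5 to 0.8. Under these the misleading pattern occurs in about 8% to 16% of trials, against about 5% for the direct contrast. The contrast fits the plan's question better, but at this sample size it supports an exploratory estimate, not a confirmatory test.

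**What to change.** In the Aim 1 Analysis Plan, name the group-by-time term, which also matches the interaction used for the sample size, and replace the sentence on pairwise comparisons with text such as:

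> The mixed model will include group, time and group-by-time. As exploratory estimates with 95% confidence intervals, we will report the group difference in change from Time 1 to Time 2 and from Time 2 to Time 3. Group differences at each visit will be reported as total effects. A nurse effect will not be inferred by comparing significance between visits. The Time 2 to Time 3 contrast assumes a stable process effect and little nurse exposure before Time 2, and its power is limited.

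Give the power beside it: about 24% to 50% for an added 0.28 SD and 60% to 94% for 0.5 SD, at assumed correlations of 0.5 to 0.8.

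First reconcile two things: the definition of Time 2 (Table 1 against section D part a), and the number of usual-care follow-ups (section D part a against Measures and Quantitative Data). The contrast cannot be computed without a usual-care Time 3.

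The cost is a few sentences and one ESTIMATE statement per contrast in Proc Mixed. No new data are needed if usual care is assessed at all three time points; if it has only one follow-up, a further assessment in that arm would be required.

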### Aim 2: Process Measures:

**Barriers and facilitators.** The patient and nurse will be contacted for exit interviews. These will be collected 5-7 days after the meta-narrative is added to the EHR. The transcribed exit interviews will be entered into ATLAS.ti, and an interpretive approach will inform the understanding of the patients' and nurses' perspectives related to barriers and facilitators. Open coding, which allows codes to form patterns as they emerge from the transcripts, will be used for the thematic analysis. An inductive approach to coding, through the use of the participant's actual words, will be used for up to three transcripts. Once the initial codes are chosen, the transcripts will be read again through an iterative process defined as "a movement back and forth through" data coding for creating thematic analyses.71(p86) As PI, I will complete the preliminary coding for each transcript then the research team will review my preliminary codes. Once the first three transcripts are coded, the research team will analyze the preliminary codes across the remainder of the transcripts. Throughout the entire analytical process, the codes will be refined. At each of the monthly research team meetings, codes can be expanded or collapsed as part of the iterative process. To ensure the rigor of the data analysis, Sandelowski's criteria for trustworthiness will be used.

**Usability testing.** Following the exit interview, the nurse participants will be asked to complete the System Usability Scale (SUS), which asks them to rank their experience and satisfaction with specific elements. Usability is defined as the relationship between humans and computers. Usability testing focuses on evaluating Instructions – How to complete the COMIRB protocol template (Social)

process measures based on four major components: user (nurse), task (utilization of meta-narrative by nurse), system (meta-narrative in EHR), and environment (inpatient nurse's station). The user-task-system-environment framework of process measures will be incorporated into the usability testing to determine barriers and facilitators from the perspective of the bedside nurse and to help determine the essential requirements for integrating the narrative intervention into the EHR by evaluating information flow, use of information, and system functionality. The process measures collected to determine usability will include: 1) field observations of the end user: the nurse; 2) chart review/log analysis of the

### **G. Summarize Knowledge to be Gained.**

The proposed work will contribute significantly to the science in the area of culturally sensitive, patient-centered palliative care interventions. As this proposed study aligns clearly with NINR's strategic focus on PC/EOL science to benefit clinical practice while improving quality of life for patient with serious illnesses, the impact of this proposed study supports research exploring interventions for optimizing quality of life.

### **Future Directions**

The K99 and R00 studies provide the developmental steps to optimize a biobehavioral intervention, providing the preliminary data required to submit an independent R01 grant in year 3 of the R00 phase. For the next steps in my research trajectory, this R01 submission will be a Phase III efficacy study of a patient-centered palliative care narrative intervention, consistent with the ORBIT model of biobehavioral intervention development. With my strong background in palliative care, both as a clinician and narrative biobehavioral intervention researcher, I will be positioned to continue building a program of research based on narrative approaches for patients living with serious illness.

